## **3. SAMPLE SIZE CONSIDERATIONS**

Restricted randomization will be used to balance the two arms of the trial in terms of prevalence of HIV, ANC volume, and rates of partner disclosure at included clinics (based on data from our prior CHIME evaluation of 141 MCH clinics). Assuming a coefficient of variation (k) of 0.2, the study has 80% power to detect a 2-fold difference in HIV incidence (between 4% and 2%) with 10 clinics per cluster and 200 women per cluster (Table 1). If targeted PrEP resulted in much better performance (67% decrease rather than 50%), 6 clinics per cluster would be sufficient. Deriving our sample size from HIV incidence difference is conservative and will enable ample statistical power to detect effects on other outcomes (such as proportion on PrEP and partner characteristics). Table 2 outlines implications of potential RCT outcomes illustrating the value of data regarding the two PrEP delivery models in scenarios with or without a significant difference in HIV incidence. We anticipate that the targeted arm may have 20% of women receiving PrEP (based on MSS risk score estimates) while the universal PrEP arm may have 5-25% of women requesting PrEP, however, these are speculative estimates. The study may not detect a difference in HIV incidence between PrEP delivery models because of appropriate PrEP uptake and use in both. However, as outlined in the contingency table (Table 2), for all scenarios the RCT would yield important data on viable approaches for delivering PrEP in pregnancy and likely

reveal a superior model in terms of the balance of effectiveness, safety, acceptability, feasibility, and cost-effectiveness.

k	HIV incidence universal	HIV incidence targeted	# women per clinic	#clinics per arm	Total # women
0.2	4%	2%	50	27	2700
0.2	4%	2%	100	15	3000
0.2	4%	2%	150	12	3600
0.2	4%	2%	200	10	4000
0.2	4%	2%	250	9	4500
0.2	4%	2%	300	8	4800
0.2	4%	1.3%	200	6	2400

	Potential HIV incidence outcome	Other potential results	Impact on programs policy in high HIV prevalence regions	Programmatically relevant data from study
Hypothesis Proved	Targeted better	Fewer women on PrEP, cost-effective, safe	Implement targeted PrEP	Data to model and compare impact on HIV transmission, cost, and scale up.
Hypothesis opposed	Universal better	Fewer women on PrEP, cost-effective, safe	Implement universal PrEP	
Mixed benefits	Universal better	Universal too many women on PrEP not cost effective	Refine universal strategy to decrease cost and unnecessary PrEP exposure	
Mixed findings	Incidence low in both, no difference	Targeted more cost-effective results in few on PrEP	Implement targeted PrEP	HIV incidence estimate/CI, cost-effectiveness, safety, process
		University more cost-effective and fewer women on PrEP	Implement universal PrEP	

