Women have persistent risk of acquiring HIV in pregnancy and postpartum and often do not perceive themselves to be at risk (1). In a meta-analysis of 19 studies including 22,803 person-years, HIV incidence in pregnant/postpartum women was 3.8 per 100 p-years, 4.7/100 p-years in pregnancy and 2.9/100 p-years postpartum (Figure 1) (2). These HIV incidence estimates are particularly high given that incidence estimation was among all women (not limited to those with seropositive partners) and appreciable HIV infection occurred despite decreased sexual activity

[figure not shown]

Figure 1: HIV Incidence in pregnancy (2)

Pregnancy and the postpartum period are characterized by dramatic hormonal and immunologic changes, changes in genital mucosa, and epithelial disruption during delivery

with decreased mucosal integrity postpartum (3-6). At the same time, sexual practices change markedly in this period. Sexual activity declines late in pregnancy and early postpartum, and male partners may seek other partners, and bring HIV back to the relationship (7-9). HIV acquisition in pregnancy/postpartum most often occurs among women who are unaware of their partner's HIV status. In Zimbabwe, among 1230 pregnant women, 239 (19%) reported their partner had been HIV tested, of whom 213 knew partner results, and 8 reported a HIV positive partner (0.6% of overall cohort). Only 1 of 14 incident HIV infections in this cohort occurred in a woman in a known serodiscordant partnership (10). Similarly, in a Kenyan cohort of 1310 pregnant women, only 1% reported knowing their partner was HIV positive, and these women had *lower* risk of HIV infection than women with unknown or reportedly HIV negative partners (11). HIV risk may be lower among the select few women who report knowing their partner's HIV-seropositive status because these partners are already on ART or use condoms. Many women do not know their partner's HIV status or believe their partner is HIV negative (12).

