For pregnant women, a risk scoring tool has also been developed to help identify those at greater HIV risk (20). This tool, developed and validated using data from 1,304 women living in Kenya, includes the following variables: Partner HIV status unknown, number of lifetime sexual partners, and history of syphilis. Women with a score >6 made up 16% of the population but accounted for 56% of HIV acquisition events.

For pregnant women, risk assessment alone may not identify all women at risk of HIV acquisition during pregnancy. Partner self-testing is a strategy that has been successfully used to identify previously unknown HIV-positive partners of pregnant women in Western Kenya. A recent study demonstrated high uptake of partner-testing when multiple self-tests are given distributed to women in antenatal care clinics along with instructions about how to use the tests and counseling about using discretion when determining whether to offer a self-test to sexual partners (21). Of women enrolled in the study, 91% (of 58 participants) reported distributing the self-test to their primary sexual partner *and* being present when their partner used the test (21). The strategy was also found safe for women who participated. This study did exclude a small number of women attending clinics who believed violence could occur from distributing the self-tests, who would likely benefit from PrEP given the risk of violence in their relationship. Including a self-testing intervention that increases partner self-testing will allow this study to identify women who may be categorized as low risk in the risk assessment but have a previously unknown HIV positive partner.

Pre-Exposure Prophylaxis (PrEP) and Women

[figure not shown]
As new studies examine topical microbicides and long-acting PrEP formulations for HIV prevention (22-25), oral PrEP remains a leading candidate for pregnancy given substantial evidence of efficacy, safety, and lack of potential for genital tract irritation that could precipitate preterm birth or ascending infection in pregnancy (26). Increasing partner ART use is another highly effective and complementary approach (27). Condoms, though effective, have not been widely adopted by pregnant/postpartum women, who are usually married and find it difficult to negotiate for condom use in the setting of a presumably stable relationship.

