coefficient of variation (k) of 0.2, the study has 80% power to detect a 2-fold difference in HIV incidence (between 4% and 2%) with 10 clinics per cluster and at least 200 women per cluster (Table 3). If targeted PrEP resulted in much better performance (67% decrease rather than 50%), 6 clinics per cluster would be sufficient. Deriving our sample size from HIV incidence difference is conservative and will enable ample statistical power to detect effects on other outcomes (such as proportion on PrEP and partner characteristics). Table 4 outlines implications of potential RCT outcomes illustrating the value of data regarding the two PrEP delivery models in scenarios with

or without a significant difference in HIV incidence. We anticipate that the targeted arm may have 20% of women receiving PrEP (based on MSS risk score estimates) while the universal PrEP arm may have 5-25% of women requesting PrEP, however, these are speculative estimates. The study may not detect a difference in HIV incidence between PrEP delivery models because of appropriate PrEP uptake and use in both. However, as outlined in the contingency table (Table 4), for all scenarios the RCT would yield important data on viable approaches for delivering PrEP in pregnancy and likely reveal a superior model in terms of the balance of effectiveness, safety, acceptability, feasibility, and cost-effectiveness.

Table 4: Contingency Table Demonstrating Implications of Potential RCT Outcomes				
	Potential HIV incidence outcome	Other potential results	Impact on programs policy in high HIV prevalence regions	Programmatically relevant data from study
Hypothesis Proved	Targeted better	Fewer women on PrEP, cost-effective, safe	Implement targeted PrEP	Data to model and compare impact on HIV transmission, cost, and scale up.
Hypothesis opposed	Universal better	Fewer women on PrEP, cost-effective, safe	Implement universal PrEP	
Mixed benefits	Universal better	Universal too many women on PrEP not cost effective	Refine universal strategy to decrease cost and unnecessary PrEP exposure	HIV incidence/CI, cost-effectiveness, safety, feasibility, process
Mixed findings	Incidence low in both, no difference	Targeted more cost-effective results in few on PrEP	Implement targeted PrEP	HIV incidence estimate/CI, cost-effectiveness, safety, process
		University more cost-effective and fewer women on PrEP	Implement universal PrEP	

d) RECRUITMENT PROCEDURES

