## 1. STUDY SUMMARY AND AIMS

**Study Purpose:** The broad objective of this study is to determine the best approach to PrEP delivery in pregnancy using existing MCH systems as a platform for efficiently delivering PrEP to pregnant women.

**Study Design:** This is a cluster randomized clinical trial with 20 ANC clinics in Western Kenya (Siaya and Homa Bay) counties comparing Universal and Targeted PrEP administration. The facility-level cluster randomization will be conducted using a restricted randomization approach based on new antenatal care clinic (ANC) volume, and County. County will be used as a proxy for County differences in HIV prevalence in the restricted randomization approach. In the Universal PrEP arm, PrEP is offered to all and women select whether they want to take it. In the Targeted PrEP arm PrEP is offered to women identified as high risk through a standardized risk assessment and partner self-testing.

**Study Population and Sites:** Twenty ANC clinics in Western Kenya (Siaya and Homa Bay) counties will be randomized, 10 Universal and 10 Targeted PrEP administration. At each clinic women attending antenatal care will be enrolled in the study. Eligibility for enrollment will include age  $\geq 15$  years, pregnancy with the gestational age up to 36 weeks by last menstrual period (LMP) or best available estimate, and tuberculosis negative, plans to reside in area for at least one year postpartum, plans to receive postnatal and infant care at the study facility, and are not currently enrolled in any other studies.

**Study Size:** At least 200 women per clinic (2,000 per ARM)

**Study Duration:** At each clinic, enrollment will occur over an approximately 10-month period (~20 HIV negative women enrolled per month) with a ~1-year period of follow-up to 9 months postpartum (time of routine measles immunizations).

**Treatment Regimen:** PrEP medication and dosing will follow the 2016 Guidelines on Use of Antiretroviral Drugs for Treating and Preventing HIV Infections in Kenya using the preferred oral TDF/FTC (300mg/200mg) once per day

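### The 80% power for HIV incidence puts the universal arm at about the no-PrEP background rate; at the plan's own PrEP uptake and cited efficacy, power is about 27–74%

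*SAP*

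**What the plan says.** SAP section 3 and protocol section 10, Component 1 c), give the same calculation. The effect to be detected is described there as a "2-fold difference in HIV incidence (between 4% and 2" per cent). The inputs are 10 clinics in each arm, 200 women in each clinic, a between-clinic k of 0.2 and a power of 80%. One more table row takes 4% against 1.3% and arrives at 6 clinics per arm; the text ties it to a larger effect: "If targeted PrEP resulted in much better performance (67% decrease rather than 50" per cent). Both documents call sizing on HIV incidence conservative.

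The same paragraph expects about 20% of women in the targeted arm to receive PrEP and 5–25% in the universal arm to request it. It calls these figures speculative and says a difference may go undetected if PrEP is used appropriately in both arms. No power is given for those uptake figures.

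Protocol section 7 a) supplies the other inputs. On background risk, "HIV incidence in pregnant/postpartum women was 3.8 per 100 p-years", with 4.7 in pregnancy and 2.9 postpartum. On the risk score, "Women with a score >6 made up 16% of the population but accounted for 56% of HIV acquisition events". Cited efficacy in women is 71% for TDF and 86% for TDF/FTC.

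**The concern.** Both arms deliver PrEP, so the comparison is between two active strategies. If the universal arm is assumed to stay at background incidence, the planned contrast is really targeted PrEP against no PrEP, and the actual contrast will be smaller.

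What is at stake is the reading of a null result. HIV infection is a primary outcome (SAP section 2). The contingency table in SAP section 3 has a row for low incidence in both arms with no difference, and it leads to adopting one model on cost-effectiveness and numbers on PrEP. A reader who believes the trial had 80% power will take a non-significant result as fair evidence that the models prevent HIV equally well. With power of 40%, it would be weak evidence of that.

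**Working it through.** **1. Reproducing the plan's table.** The alpha level is not stated; I assumed two-sided 0.05. With m women per clinic and c clinics per arm:

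c = a + (1.96 + 0.84)² × [p0(1−p0)/m + p1(1−p1)/m + k²(p0² + p1²)] / (p0 − p1)²

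For p0 = 0.04, p1 = 0.02, m = 200, k = 0.2, the bracket is 0.00029 + 0.00008 = 0.00037. With a = 2 (the matched or stratified form), c = 2 + 7.849 × 0.00037 / 0.0004 = 9.26, rounded up to 10. The seven rows give 26.33, 14.95, 11.16, 9.26, 8.12, 7.36 and 5.52, which round up to the plan's 27, 15, 12, 10, 9, 8 and 6. With a = 1 the 200-women row gives 9 clinics, so a = 2 is the form that matches. Power at exactly 10 clinics is 83.7% (a = 2) or 87.7% (a = 1).

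**2. Where the 4% sits.** Assume entry at 24 weeks, delivery at 40 weeks and follow-up to 9 months: 16/52 + 0.75 = 1.06 years.
- At 3.8 per 100 person-years: 1 − exp(−0.038 × 1.06) = 3.9%.
- At 4.7 then 2.9: 1 − exp(−(0.047 × 0.308 + 0.029 × 0.75)) = 3.6%. Entry at 20 weeks gives 3.9%.

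So 4% is about the background rate in the documents. That is an inference, since neither document says where the 4% comes from.

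**3. Incidence net of PrEP in each arm.** Let E be efficacy and u the universal-arm uptake. Assume universal users have average risk and every flagged woman takes PrEP.
- Universal: 4% × (1 − u × E)
- Targeted: 4% × (1 − 0.56 × E)

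At E = 0.86 the targeted arm is 4% × (1 − 0.482) = 2.07%; at E = 0.71 it is 4% × (1 − 0.398) = 2.41%.

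**4. Power.** Power = Φ(√[(10 − a)(p0 − p1)² / bracket] − 1.96). Example at E = 0.86, u = 0.25: rates 3.14% and 2.07%, bracket 0.000310, √(8 × 0.010664² / 0.000310) = 1.71, power 40%.

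| Efficacy | Targeted | Universal at 5 / 15 / 25% uptake | Power, a = 2 | Power, a = 1 |
|---|---|---|---|---|
| 71% | 2.41% | 3.86 / 3.57 / 3.29% | 55 / 41 / 27% | 60 / 45 / 30% |
| 86% | 2.07% | 3.83 / 3.48 / 3.14% | 74 / 59 / 40% | 79 / 64 / 44% |
| 90% | 1.98% | 3.82 / 3.46 / 3.10% | 79 / 64 / 44% | 83 / 69 / 49% |
| 96% | 1.85% | 3.81 / 3.42 / 3.04% | 85 / 71 / 51% | 88 / 76 / 56% |

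Powers come from unrounded rates and allow for no loss to follow-up. At 86% efficacy, 80% power would need 12, 16 and 24 clinics per arm (a = 2).

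**5. Sensitivity.** With 80% uptake among flagged women (my assumption) and 86% efficacy, power is 50, 33 and 18%. If universal users carried 30% of infections instead of being unselected (also my assumption), the universal arm would be 4% × (1 − 0.30 × 0.86) = 2.97% and power 31%.

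**6. The 67% row.** A fall from 4% to 1.3% is 67.5%. Through the score it needs uptake × efficacy = 0.675 / 0.56 = 1.21, which exceeds 1.

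**The case against.** A reader might infer that a 50% reduction is beyond anything the plan's inputs allow. The documents do not support that. The protocol also cites efficacy above 90% at high adherence, and a 96% reduction in a project combining PrEP with partner ART. With full flagged uptake these give 0.56 × 0.90 = 50.4% and 0.56 × 0.96 = 53.8%. The 96% is generous for PrEP alone, but the targeted arm does refer partners found HIV-positive for treatment.

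Nor is 56% a strict ceiling. Women scoring 6 or less may ask for PrEP, and women whose partners refuse the self-test are counselled again at visit 2. The plan expects 20% on PrEP against 16% flagged. If the extra 4% carry average low-risk incidence, coverage is 0.56 + 0.04 × 0.44/0.84 = 58%, and 86% efficacy gives a 50% reduction. This stands, but it does not restore the power: at 58% coverage and 86% efficacy, power is 78, 63 and 45% (a = 2).

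It is also fair that the plan discloses that it may find no difference (again in protocol section 13), and that its contingency table lists the incidence estimate and CI as an output. The 67% row is conditional and does not set the sample size. But the disclosure carries no number, attributes a null to good PrEP use in both arms, and sits beside the description of the sample size as conservative.

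**Conclusion.** The concern holds in a limited form. The sample-size arithmetic is right, and 80% is a correct conditional figure for 4% against 2%. The weakness is the 4%: it matches background incidence, in an arm where the plan itself expects 5–25% PrEP use.

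At the cited 71–86% efficacy, power for HIV incidence is about 27–74% with the formula that reproduces the plan's table, and 3–5 points higher with the alternative. About 80% needs universal uptake near 5%, near-complete flagged uptake and efficacy of about 90% or more. The 67% row cannot be reached through score-guided PrEP alone and must rely on other effects.

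These figures assume that 4% is background, that flagged women carry 56% of infections and all take PrEP, that universal use is unrelated to risk, and that efficacy is equal in both arms. Less than full flagged uptake, or universal users at higher than average risk, would lower power. Partner testing and partner ART could raise it by an amount the documents do not give for this trial. So the documents do not show that the trial cannot reach 80% power, only that most of the plan's stated range falls short of it.

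**What to change.** Keep the 4,000 women and change SAP section 3 and the matching protocol text:
- State the source of the 4% and whether it allows for PrEP use in the universal arm.
- Add power rows over the plan's uptake and efficacy ranges, for example, at 86% efficacy, 3.83% against 2.07% (74%), 3.48% against 2.07% (59%) and 3.14% against 2.07% (40%), with the assumptions listed.
- Say that the 67% row depends on effects beyond score-guided PrEP, and qualify the description of the sample size as conservative.
- State, in the text and beside the no-difference row of the contingency table, that a non-significant HIV result will be read through its confidence interval and not as evidence of no difference.

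The cost is wording and table rows. The stated power becomes less favourable, and nothing changes in recruitment or conduct.

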During the past decade, legal, ethical, and policy deliberations have informed a vision to accelerate access to effective interventions for pregnant women and their children (64). Pregnant women currently receive several preventive interventions, including anti-malarials, PMTCT, and TB-prevention (if HIV infected). For some interventions (malaria prophylaxis and early PMTCT), pregnancy implementation was informed by RCTs conducted in pregnant women and their infants with most benefits for the infant. For other interventions (isoniazid in HIV-infected women), efficacy evidence was extrapolated from non-pregnant adult studies and safety data was obtained from observational studies. The level of safety evidence for PrEP (no animal fetal toxicity, thousands of infants exposed to TDF/FTC PMTCT, hundreds to PrEP in early pregnancy) led WHO, CDC, and the Kenyan Ministry of Health (MoH) to permit PrEP use in pregnancy (61, 65, 66). WHO early-release guidelines (Sept 2015) recommend PrEP for anyone at 'substantial HIV risk', and noted need for research on PrEP in pregnancy and lactation (66), and updated WHO guidance from 2017 recommended the use of PrEP in pregnancy and lactation, although important safety and implementation gaps remain. Implementation science studies can provide a framework to increase accrual of safety and effectiveness data of PrEP in pregnancy while refining programmatic strategies.

8) RATIONALE

In a region with 15-20% HIV prevalence, an estimated 20% of HIV-uninfected women could have HIV exposures in pregnancy. In a theoretical scenario of perfect PrEP coverage, all women at risk receive PrEP while no women not at HIV risk receive PrEP (Figure 4). With mandatory PrEP

[figure not shown]

Figure 4: Potential PrEP in pregnancy, delivery strategies. Measuring uptake, process, and HIV incidence, we can inform the best health systems model for PrEP delivery in pregnancy.

given to all women (similar to the approaches used for malaria prophylaxis), all women at risk would be covered but many women not at risk receive unnecessary PrEP. Our premise is that a targeted PrEP model may be closer to perfect coverage than a universal offer/self-select model. Implementing targeted PrEP through strategies that include facilitation of partner testing with self-tests could add HIV prevention benefit by increasing partner HIV diagnosis and treatment similar to the initiation of PrEP among pregnant women. By implementing these strategies and

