### Primary Aims:

**AIM 1a:** To compare Universal PrEP to Targeted PrEP for outcomes reflecting the balance of PrEP effectiveness and safety:

1. HIV incidence at 9 months postpartum
2. Proportion of women who accepted PrEP

**Sub-Aim 1a.** To compare infant outcomes (growth, birth outcomes, HIV status) between PrEP users and nonusers in combined trial arms.

**AIM 1b:** To compare trial arms for:

1. Proportion of women 'appropriately' on PrEP (based on risk factors)
2. PrEP adherence (DBS) and duration
3. Partners with known HIV status, on ART

**AIM 2:** Health economic evaluation of targeted vs. universal PrEP

**AIM 3:** Assessment of barriers and facilitators of PrEP delivery strategies at the individual patient, healthcare facility, and organizational level

*This analysis plan will focus on Aim 1 except for sub-aim 1a which is in a separate SAP for birth/infant outcomes.*

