## **5. STATISTICAL ANALYSES AND DESCRIPTION OF MAIN TABLES**

**AIM 1a:** The proportion of all women enrolled in the study who use PrEP (proportion of women exposed to PrEP) will be compared between trial arms using GEE with a binomial link.

**AIM 1b:** The proportion with 'appropriate' use will be compared between arms using GEE with a binomial link. PrEP adherence will be measured among women on PrEP using DBS TFV drug levels. All women receiving PrEP will have 3-monthly DBS samples available. For each trial arm (10 clinic-cluster) a random subset of 220 DBS will be assessed. TFV drug levels will be compared by trial arm using GEE with a Gaussian link. PrEP duration will be computed for each woman based on self-report and pharmacy records and average duration compared between arms using GEE with a Gaussian link. Reported and confirmed partner with HIV status, proportions of partner HIV positive, unknown and HIV negative status, and reported and confirmed partner ART use will be compared between arms using GEE with a binomial link.

Infant outcomes: mean birthweight and serial weight-for-age z-scores (WAZ), height-for-age z-scores (HAZ), and weight-for-height z-scores (WHZ) will be compared between trial arms using GEE with a Gaussian link. A separate analysis will assess birth and infant outcomes by PrEP exposure in the combined arms.

**AIMS 2-4** will be conducted after the primary analysis and will not be reviewed by the EAC.

---

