**Table 2. Primary and secondary endpoints**

	N (%) or incidence/100 py			RR (95% CI), p-value
	All subjects	Trial arm		
		Universal	Targeted	
Primary outcomes				
HIV incidence				
Initiated on PrEP				
Secondary endpoints				
'Appropriately' on PrEP (based on risk score)				
Partner known HIV status by end of follow-up				
Partner on ART if HIV infected				
TFV-DP levels (median on random sample)				

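### Power is called ample for partner characteristics, but this is unsupported for partner ART among known HIV-positive partners, a denominator that the intervention itself changes

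*SAP*

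**What the plan says.** SAP section 3, and the protocol's sample size section under Component 1, size the trial on HIV incidence: 4% against 2%, k = 0.2, 10 clinics per arm, 200 women per clinic. Both add that this "will enable ample statistical power to detect effects on other outcomes (such as proportion on PrEP and partner characteristics". Neither gives a calculation for any other outcome.

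Partner ART enters the plan in three places:
- SAP Aim 1b lists "Partners with known HIV status, on ART".
- SAP section 5 says that "reported and confirmed partner ART use will be compared between arms using GEE with a binomial link" and names no denominator.
- The SAP appendix table of primary and secondary endpoints has the row "Partner on ART if HIV infected", in a table whose last column is a risk ratio with confidence interval and p-value.

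The protocol's literature review cites two pregnancy cohorts. In one, of 1,230 women, "8 reported a HIV positive partner (0.6% of overall cohort"; the other reads "in a Kenyan cohort of 1310 pregnant women, only 1% reported knowing their partner was HIV positive". It suggests that such women may be at lower risk "because these partners are already on ART or use condoms".

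Protocol section 8 says that targeted delivery with partner self-tests "could add HIV prevention benefit by increasing partner HIV diagnosis and treatment", and the Aim 1b hypotheses expect more partners on ART in the targeted arm. Self-test kits are offered only in targeted clinics. A referral letter and clinic-based partner testing are available in both arms.

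**The concern.** The sample size rests on an outcome measured in all 2,000 women per arm. The partner ART row uses only women with a partner known to be HIV-positive, who may be few, so the assurance of ample power does not carry over to it.

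There is a second, separate issue. Because only one arm receives self-tests, randomisation itself affects who enters the denominator. If the additional partners are treated less often than those already known, the proportion on ART can fall in the targeted arm while the number on ART rises. The row could then point away from the Aim 1b hypothesis when that hypothesis is true. A null result could rest on a small universal-arm group while the plan describes power as ample.

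**Working it through.** **The plan's own figure.** With two-sided alpha 0.05 (not stated; assumed), clinics per arm = 2 + 7.849 × [p0(1−p0)/m + p1(1−p1)/m + k²(p0² + p1²)]/(p0−p1)², where 7.849 = (1.96 + 0.8416)². For 4% vs 2%, m = 200, k = 0.2: the bracket is 0.000192 + 0.000098 + 0.00008 = 0.00037; 7.849 × 0.00037/0.0004 = 7.26; adding 2 gives 9.26, so 10 clinics. The same formula reproduces all seven rows (27, 15, 12, 10, 9, 8, 6). The incidence calculation is not in question.

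**Size of the denominator.** 2,000 × 8/1,230 = 13.0; 2,000 × 1% = 20. (The printed 0.6% gives 12.) This describes women without this trial's partner-testing procedures, so it fits the universal arm at most and is a floor for the targeted arm.

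**Power, no clustering.** Φ(|p0−p1|/√(p0q0/n0 + p1q1/n1) − 1.96). The documents give no ART rates; 60% vs 80% is assumed.
- 13 per arm: 0.2/√(0.40/13) = 1.140; power 21% (Fisher's exact test 11%).
- 20 per arm: 0.2/√(0.40/20) = 1.414; power 29% (Fisher 19%).
- 20 universal, 400 targeted: 0.2/√(0.24/20 + 0.16/400) = 1.796; power 44% with 60% in the universal arm. With 80% there, 0.2/√(0.16/20 + 0.24/400) = 2.157; power 58%. The universal arm is the bottleneck.
- Needed for 80% power: 7.849 × 0.40/0.04 = 78.5, so 79 per arm, about 4% of women.

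Other assumed differences need 59 per arm (70% vs 90%) or 36 per arm (50% vs 80%).

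**With clustering.** Power is Φ(√(9(p0−p1)²/V) − 1.96), where V is the bracket above with m the contributing women per clinic, and 9 is 10 clinics less 1. k = 0.2 is borrowed from the incidence calculation. At 80 per arm, V = 0.05 + 0.04 = 0.09 and power is 52%, against 81% unclustered. At 400 per arm (the 20% of women whom protocol section 8 estimates could be exposed), V = 0.01 + 0.04 = 0.05 and power is 77%.

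**Direction.** Suppose each arm has K already-known positive partners, a proportion a of them on ART, and self-tests add X partners in the targeted arm, a proportion r of them on ART. The conditional proportion is a in the universal arm and (Ka + Xr)/(K + X) in the targeted arm, which is below a whenever r < a. The count on ART rises by Xr. If the referral letter finds some partners in the universal arm too, the same holds provided that the targeted arm finds more.

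Assumed values, with K = 20:

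| a | X | r | Universal | Targeted | Conditional RR | RR over 2,000 women per arm |
|---|---|---|---|---|---|---|
| 80% | 20 | 70% | 16/20 | 30/40 | 0.94 | 1.88 |
| 80% | 40 | 50% | 16/20 | 36/60 | 0.75 | 2.25 |
| 80% | 100 | 30% | 16/20 | 46/120 | 0.48 | 2.88 |
| 60% | 40 | 70% | 12/20 | 40/60 | 1.11 | 3.33 |

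The last row shows that there is no reversal when r exceeds a.

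**Power of the all-women outcome.** Same clustered formula, m = 200, with the 9 replaced by 8 for the lower value of each pair. For 0.8% vs 1.8% (16 and 36 of 2,000): 71% to 76% at k = 0, 66% to 71% at k = 0.2, 54% to 59% at k = 0.4. For 0.8% vs 1.1% (20 found, 30% on ART): 12% to 15% across those values of k.

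**The case against.** The 0.6% and 1% are background figures, not design inputs. Both arms offer a referral letter and clinic testing, universal-arm counselling encourages women to bring untested partners, and status is assessed by the end of follow-up, so the trial may identify more positive partners than those cohorts did. This stands: the size point is conditional. A reader might infer that 13 to 20 women will contribute in each arm. The documents do not support that, and the direction argument itself needs a larger targeted-arm denominator.

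The ART rates are assumed, and the protocol's remark about partners already on ART is only a possible explanation. This also stands. A reader might infer that the trial will report the wrong direction; the documents show only that it can.

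The shell table gives N (%) by arm, and section 5 also compares partner status categories, so the larger count and the shift in denominator would be partly visible. That softens the point, but the risk ratio and p-value would still be computed on the conditional proportion.

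Partner ART is absent from the secondary outcome list in SAP section 2 and from protocol Table 7. That limits its weight, but Aim 1b, section 5 and the shell table still commit to comparing it.

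Finally, ART coverage among diagnosed partners is a legitimate question, and an all-women outcome has a bias of its own: disclosure of a partner already on ART counts as an event with no new treatment. Both are fair, and the fix has to state them.

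**Conclusion.** The assurance of ample power is unsupported for partner ART among known HIV-positive partners. If the universal arm resembles the cited cohorts, power for an assumed 60% vs 80% is about 21% to 29% with equal arms and 44% to 58% with 400 targeted-arm women, before clustering. If about 4% or more of women in each arm know of a positive partner, the size point largely goes before clustering is allowed for.

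The direction point does not depend on those cohort rates. It needs the targeted arm to find more positive partners, and newly found partners to be on ART less often than known ones. The second condition is plausible but undocumented.

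Two wider readings are not supported. The incidence sample size is not wrong. Nor does the point extend to partner HIV status known, which is measured in all women.

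**What to change.** - In SAP section 5 and the shell table of primary and secondary endpoints, make the between-arm comparison *partner known HIV-positive and on ART*, over all enrolled women, with the same GEE.
- Keep ART among known-positive partners as a descriptive row by arm, with n, split by status known at enrolment or learned later, and with no between-arm p-value.
- State that the all-women outcome combines finding, disclosure and treatment, so it can rise in the targeted arm through disclosure of partners already on ART.
- In SAP section 3 and the protocol, limit the claim of ample power to common outcomes measured in all women (PrEP uptake, partner HIV status known), and say that power for partner ART is not assured with either denominator.

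The cost is one denominator, one table row and a reworded sentence in each document; no added women, clinics or data. The downside is that the all-women outcome does not isolate linkage to treatment, and its own power is modest, as shown above.
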